8.2.2 Specimen Preparation, Handling and Shipping

Appropriate blood and secretion precautions will be employed by all personnel in the drawing of blood and shipping and handling of all specimens for this study, as currently recommended by the Centers for Disease Control and Prevention and the National Institutes of Health. All potentially infectious specimens will only be transported locally to the laboratory using packing mandated in the Code of Federal Regulations, 42 CFR Part 72 and IATA guidelines.

8.2.3 Instructions for Specimen Preparation, Handling, and Storage

Any residual serum from safety screening, aliquots of stool, and parasite DNA extracted from the stool of enrolled subjects only will be stored in cryovials marked with the subject identification number and date of specimen collection at icddr,b or Rajshahi Hospital or Clinic following specific consent of the subjects. Long-term stored specimens will go to the Fisher Repository. Future studies may include measuring gold levels in the blood or stool. Other researchers may request access to these specimens for collaborative studies as well. Further instructions for specimen preparation, handling, and storage are included in the protocol-specific MOP as appropriate. There will be no human DNA collection or storage.

8.2.4 Specimen Shipment

Only noninfectious, parasite extracted DNA specimens will be shipped to UCSD for quantitative parasite loads or University of Virginia for genotyping. They can be sent at room temperature by standard international couriers, or designated members of the study team with completed specimen/Transport Receipt Logs. The residual long-term stored specimens will be shipped according to IATA guidelines to the Fisher Repository.

9 ASSESSMENT OF SAFETY

9.1 Specification of Safety Parameters

Because this is an FDA approved drug that has been in use for more than 25 years, the potential AEs have been well documented in subjects in longer term therapy for rheumatoid arthritis. Of the AEs listed on the Insert, the most serious reactions would be an allergic reaction to gold, which could include anaphylactic reactions, necrotizing enterocolitis, pulmonary fibrosis, exfoliative dermatitis, bone marrow aplasia or other severe hematologic disorders.

The adverse reactions incidences listed below are based on observations of 1) 4,784 Ridaura-treated subjects in clinical trials (2,474 U.S., 2,310 foreign), of whom 2,729 were treated more than one year and 573 for more than three years; and 2) post-marketing experience. The highest incidence is during the first six months of treatment; however, reactions can occur after many months of therapy. With rare exceptions, all subjects were on concomitant nonsteroidal anti-inflammatory therapy; some of them were also taking low dosages of corticosteroids. Reactions occurring in more than 1% of Ridaura-treated patients:

- *Gastrointestinal*: loose stools or diarrhea (47%); abdominal pain (14%); nausea with or without vomiting (10%); constipation; anorexia*; flatulence*; dyspepsia*; dysgeusia.
- *Dermatological*: rash (24%); pruritus (17%); hair loss; urticaria.
- *Mucous Membrane*: stomatitis (13%); conjunctivitis*; glossitis.
- *Hematological*: anemia; leukopenia; thrombocytopenia; eosinophilia.
- *Renal*: proteinuria*; hematuria.
- *Hepatic*: elevated liver enzymes.

*Reactions marked with an asterisk occurred in 3-9% of the patients. The other reactions listed occurred in 1-3%. Reactions occurring in less than 1% of Ridaura-treated patients

- *Gastrointestinal*: dysphagia; gastrointestinal bleeding†; melena†; positive stool for occult blood†; ulcerative enterocolitis.

9.2 Methods and Timing for Assessing, Recording, and Analyzing Safety Parameters

9.2.1 Adverse Events

Adverse Event: International Conference on Harmonisation (ICH) E6 defines an AE as any untoward medical occurrence in a patient or clinical investigation subject administered a pharmaceutical product regardless of its causal relationship to the study treatment. An AE can therefore be any unfavorable and unintended sign (including an abnormal laboratory finding), symptom, or disease temporally associated with the use of a medicinal (investigational) product. The occurrence of an AE may come to the attention of study personnel during study visits and interviews of a study recipient presenting for medical care, or upon review by a study monitor.

AEs not meeting the protocol-defined criteria for SAEs will be captured on the appropriate data collection form and electronic case report form (eCRF). Information to be collected for unsolicited AEs includes event description, date of onset, licensed clinician's assessment of severity and relationship to study product and alternate etiology (if not related to study product) (assessed only by those with the training and authority to make a diagnosis and listed on the Form FDA 1572 as the site principal investigator or sub-investigator), date of resolution of the event, seriousness and outcome. AEs while on study will be documented appropriately regardless of relationship. AEs will be followed to resolution.

Any medical condition that is present at the time that the subject is screened will be considered as baseline and not reported as an AE. However, if the severity of any pre-existing medical condition increases, it will be recorded as an AE.

AEs must be graded for severity and assessed for relationship to study product (see definitions below). Adverse events characterized as intermittent require documentation of onset and duration of each episode. The start and stop date of each reported AE will be recorded on the appropriate data collection form and eCRF.

FDA defines an AE as any untoward medical occurrence associated with the use of a drug in humans, whether or not considered drug related.

Severity of Event: AEs will be assessed by a licensed study physician listed on the Form FDA 1572 as the site principal investigator or appropriate sub-investigator using a protocol-defined grading system (see Section 9.2.2 and 9.2.3). For events not included in the protocol-defined grading system, the following guidelines will be used to quantify severity:

- Mild (Grade 1): Events require minimal or no treatment and do not interfere with the subject's daily activities.
- Moderate (Grade 2): Events result in a low level of inconvenience or concern with therapeutic measures. Moderate events may cause some interference with functioning and daily activities.
- Severe (Grade 3): Events that prevent the subject's usual daily activities and may require systemic drug therapy or other treatment. Severe events are usually incapacitating.

The severity of systemic and clinical laboratory adverse events will be graded according to Section 9.2.2 and the toxicity tables included in the Appendices to this protocol.

Changes in the severity of any AE will be documented to allow an assessment of the duration of the event at each level of intensity. When AEs are intermittent, the onset and duration of each episode will be documented.

Relationship to Study Products: The study physician's assessment of an AE's relationship to study product is part of the documentation process, but it is not a factor in determining what is or is not reported in the study. If there is any doubt as to whether a clinical observation is an AE, the event should be reported. The relationship to study product must be assessed for AEs using the terms: related or not related. In a clinical trial, the study product must always be suspect. To help assess, the following guidelines are used:

- Related – There is a reasonable possibility that the study product caused the adverse event. Reasonable possibility means that there is evidence to suggest a causal relationship between the study product and the adverse event.
- Not Related – There is not a reasonable possibility that the administration of the study product caused the event.

9.2.2 Solicited Events

Solicited events are AEs that are known to occur with this study product. Solicited AEs will not be collected that are related to any prescribed metronidazole. The below Toxicity Grading Scales will be used to grade events.

Adverse event data will be collected at each visit using specific questions and/or targeted physical examination. Based on the adverse reactions listed on the package insert, expected side effects include: loose stools or diarrhea, abdominal pain, nausea with or without vomiting, constipation, anorexia, flatulence, dyspepsia, dysgeusia, pruritus, hair loss, urticarial, stomatitis, conjunctivitis,

glossitis, and hematuria. Diarrhea, however, will not be recorded as a side effect because all participants will enroll with diarrhea, and because its resolution is the endpoint of the study. Physical examinations will look for abdominal pain, hair loss, urticaria, rashes, stomatitis, conjunctivitis, and glossitis. Hematologic, renal, or hepatic laboratory abnormalities will be picked up on testing at Day 7. Adverse event collection will continue until Day 28 (following three half-lives of the drug).

Event	Mild (Grade 1)	Moderate (Grade 2)	Severe (Grade 3)
Loose stools or diarrhea	Does not interfere with daily activity	Interferes with daily activity	Prevents daily activity (incapacitating)
Abdominal Pain	Does not interfere with daily activity	Interferes with daily activity	Prevents daily activity (incapacitating)
Nausea with or without vomiting	Does not interfere with daily activity	Interferes with daily activity	Prevents daily activity (incapacitating)
Constipation	Does not interfere with daily activity	Interferes with daily activity	Prevents daily activity (incapacitating)
Anorexia	Does not interfere with daily activity	Interferes with daily activity	Prevents daily activity (incapacitating)
Flatulence	Does not interfere with daily activity	Interferes with daily activity	Prevents daily activity (incapacitating)
Dyspepsia	Does not interfere with daily activity	Interferes with daily activity	Prevents daily activity (incapacitating)
Dysgeusia	Does not interfere with daily activity	Interferes with daily activity	Prevents daily activity (incapacitating)
Pruritus	Does not interfere with daily activity	Interferes with daily activity	Prevents daily activity (incapacitating)
Hair loss	Does not interfere with daily activity	Interferes with daily activity	Prevents daily activity (incapacitating)
Urticaria	Does not interfere with daily activity	Interferes with daily activity	Prevents daily activity (incapacitating)
Stomatitis	Does not interfere with daily activity	Interferes with daily activity	Prevents daily activity (incapacitating)
Conjunctivitis	Does not interfere with daily activity	Interferes with daily activity	Prevents daily activity (incapacitating)
Glossitis	Does not interfere with daily activity	Interferes with daily activity	Prevents daily activity (incapacitating)

Event	Mild (Grade 1)	Moderate (Grade 2)	Severe (Grade 3)
Hematuria	Does not interfere with daily activity	Interferes with daily activity	Prevents daily activity (incapacitating)
Rash	Does not interfere with daily activity	Interferes with daily activity	Prevents daily activity (incapacitating)

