7.3 Follow-up Visits

This section summarizes the follow-up procedures conducted for each subject. Complete details for each Study Day are provided in Appendix A. Visit windows are specified around the target for each visit. Follow-up visits are scheduled in reference to dosing dates as indicated for each visit window. Subjects will be enrolled at the icddr,b or Rajshahi Medical College Hospitals and have follow-up visits in the Hospital until their diarrhea has resolved. Subsequent follow-up visits may be held at the icddr,b, Rajshahi Hospital, or clinic or their home except for Visit 07 which must be at icddr,b or Rajshahi Hospital or clinic because blood drawing is required. When a visit falls on a holiday Friday, two days' supply of study product will be given on Thursday and the Friday dose will be self-administered as instructed and documented upon the next visit. Staff will notify the subject on Friday to take the dose and document it was taken. The window for stool specimens will be +1 day and the date of collection noted. For visits that fall on a Friday, the study team member will confirm on the next scheduled visit the diarrhea status as noted on the Visit Documentation for the **missed** visit. This will be submitted in the Data System for study end-point analysis.

7.3.1 Visit 02, Day 2

- Targeted physical exam performed, if indicated.
- 2 capsules of study product (6mg total) or placebo will be orally taken by the subject.
- Assessment of any side effects or adverse events.
- Any subject with worsening diarrhea as assessed by the study physician, may have their dose discontinued and receive standard of care metronidazole.
- Medical history, including any concomitant medications, reviewed.

7.3.2 Visit 03, Day 3

- Targeted physical exam performed, if indicated.
- 2 capsules of study product (6mg total) or placebo will be orally taken by the subject.
- Assessment of any side effects or adverse events.
- Any subject with worsening diarrhea as assessed by the study physician, may have their dose discontinued and receive standard of care metronidazole.

- Medical history, including any concomitant medications, reviewed.
- Stool sample will be collected for ova and parasite testing. The window for stool specimens will be +1 day and the date of collection noted.

7.3.3 Visit 04, Day 4

- Targeted physical exam performed, if indicated.
- 2 capsules of study product (6mg total) will be orally taken by the subject.

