9.2.4 Serious Adverse Events

An adverse event or suspected adverse reaction is considered “serious” if, in the view of either the investigator or sponsor, it results in any of the following outcomes:

- Death,
- a life-threatening adverse event*,
- inpatient hospitalization or prolongation of existing hospitalization,
- a persistent or significant incapacity or substantial disruption of the ability to conduct normal life functions, or
- a congenital anomaly/birth defect.
- Important medical events that may not result in death, be life-threatening, or require hospitalizations may be considered serious when, based upon appropriate medical judgment they may jeopardize the patient or subject and may require medical or surgical intervention to prevent one of the outcomes listed in this definition. Examples of such medical events include allergic bronchospasm requiring intensive treatment in an emergency room or at home, blood dyscrasias or convulsions that do not result in inpatient hospitalization, or the development of drug dependency or drug abuse.

* Life-threatening adverse event. An adverse event is considered “life-threatening” if, in the view of either the investigator or sponsor, its occurrence places the patient or subject at immediate risk of death. It does not include an adverse event, had it occurred in a more severe form, might have caused death.

All SAEs will be:

- recorded on the appropriate AE eCRF
- followed through resolution by a study clinician
- reviewed and evaluated by a study clinician

9.2.5 Procedures to be Followed in the Event of Abnormal Laboratory Test Values or Abnormal Clinical Findings

The site principal investigator or appropriate co-investigator is responsible for reporting all AE/SAEs that are observed or reported during the study, regardless of the relationship to study product. AE/SAEs, abnormal clinical laboratory test values, or abnormal clinical findings will

be documented, reported, and followed until levels return to baseline or until the abnormal value is determined to be not clinically significant.

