11.2 Sample Size Considerations

The primary amebiasis outcome for this study is to compare the proportion of subjects with resolution of diarrhea (less than 3 loose stools/ 24 hours) by Day 7 of therapy, in which placebo is expected to have a clearance rate of approximately 15-20%. Sample size calculations for both primary endpoints are based on a two-sample, two-sided binomial test for proportions, with alpha set to 0.05. Calculations are performed using the R statistical package (Version 3.0.2; <http://www.r-project.org>). The primary amebiasis endpoint in this aim is to compare the resolution of diarrhea between the two study arms to demonstrate that auranofin increases

resolution of diarrhea. For this power analysis, we assume the following: a predicted diarrhea resolution rate of at least 80% (based on treatment results with current standard therapy with metronidazole, Pherson, 1984) in the auranofin treatment group.

With these assumptions, assuming 10% attrition (determined from the average of multiple other clinical trials in the same districts), a sample size of 68 with amebiasis (34 per arm; 60 completers in total) achieves greater than 95% power to detect a difference between the group proportions of 60%. The high statistical power for the primary endpoint is planned to also ensure adequate power for the secondary endpoints.

For the primary giardiasis endpoint of proportion of subjects with resolution of diarrhea by Day 5, a similar sample size of 34 per arm will achieve 85% power to detect a 40% difference between treatment arms with a predicted clearance rate of 70% (based on response rates to metronidazole or tinidazole, Gardiner, 2001) and a 30% clearance rates in placebo.

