Solicited events are AEs that are known to occur with this study product. Adverse event data is collected at each visit using specific questions and/or targeted physical examination. Based on the adverse reactions listed on the package insert, these include: loose stools or diarrhea, abdominal pain, nausea with or without vomiting, constipation, anorexia, flatulence, dyspepsia, dysgeusia, pruritus, hair loss, urticarial, stomatitis, conjunctivitis, glossitis, hematuria, and rashes. As noted above, diarrhea is considered an adverse event only in the asymptomatic population as it is a condition for enrollment in the symptomatic population. Physical examinations look for abdominal pain, hair loss, urticaria, rashes, stomatitis, conjunctivitis, and glossitis. In the symptomatic population, solicited AEs are not collected that are related to any prescribed metronidazole. Adverse event collection continues until Day 28 (following three half-lives of the drug). Each solicited adverse event described above is graded as Mild (Grade 1) if it “Does not interfere with daily activity”, as Moderate (Grade 2) if it “Interferes with daily activity”, and as Severe (Grade 3) if it “Prevents daily activity (incapacitating)”. Grading for vital signs, also collected on every visit, is given in [Table 6](#). Furthermore, hematology, biochemistry, and urine labs are analyzed on Study Day 7. Grading for these adverse events is given in [Table 7](#). Some laboratory grading ranges were modified in protocol updates; these modifications are displayed in the table. Laboratory results are graded according to the protocol effective on the date the sample was collected. The effective date is the date that the site received IRB approval for the version and began implementing that version. (The effective date is later than the protocol version date, which indicates when the version was approved by DMID.) The first subjects in the study enrolled under Protocol Version 4.0, so laboratory ranges for earlier protocol versions are not displayed. The effective dates are as follows: Version 4.0: 18Oct2016, Version 5.0: 12Dec2017, Version 6.0: 07Aug2018, Version 7.0: 23Jul2019.

Table 6: Vital Signs Grading Scale

Vital Signs*			
Vital Signs	Mild (Grade 1)	Moderate (Grade 2)	Severe (Grade 3)
Fever (°C) **	37.8-38.4	38.5-38.9	>= 39.0
Hypertension (systolic) mm Hg	141-150	151-155	>155 or an ER visit or hospitalization for malignant hypertension

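### Dropping solicited adverse events attributed to metronidazole conflicts with the protocol's general reporting rules and can distort the by-arm solicited-event tables in either direction

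*Protocol*

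**What the plan says.** Protocol 9.2.2 defines solicited events as those known to occur with auranofin and then excludes some of them: "Solicited AEs will not be collected that are related to any prescribed metronidazole". SAP 4.5.1 carries the rule over: "In the symptomatic population, solicited AEs are not collected that are related to any prescribed metronidazole".

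Three other statements bear on it. Protocol 9.2.1 says "AEs while on study will be documented appropriately regardless of relationship". Protocol 9.2.5 makes the site investigator responsible for "reporting all AE/SAEs that are observed or reported during the study, regardless of the relationship to study product". Protocol 9.2.1 also says of the physician's assessment of relationship to study product that "it is not a factor in determining what is or is not reported in the study".

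On who receives metronidazole, the visit descriptions from Day 2 to Day 14 in Protocol 7.3 say: "Any subject with worsening diarrhea as assessed by the study physician, may have their dose discontinued and receive standard of care metronidazole". Solicited collection runs past any such rescue: "Adverse event collection will continue until Day 28". The Day 30 standard-of-care treatment comes after collection ends and is not at issue.

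SAP 9.3.1 and Tables 35-36 show the number, percentage and 95% confidence interval of subjects with each solicited event by arm, with no provision for rescue.

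**The concern.** An event blamed on metronidazole is, by that judgment, not related to study product. Protocol 9.2.1 and 9.2.5 require it to be recorded; Protocol 9.2.2 and SAP 4.5.1 say not to collect it. The SAP takes precedence over the protocol's statistical section, but it repeats the exclusion and so does not settle the matter.

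The exclusion acts only on subjects who received metronidazole, a group formed after randomization by the course of their diarrhea. It depends on a judgment for which no criteria are given. The event being judged is by definition one that auranofin can cause, and the assessor may have recognised the capsules (Protocol 5.3.2). At stake is whether Tables 35-36 show the true solicited-event incidence by arm. An event never collected cannot be restored at analysis.

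**Working it through.** **Text check.** Take a non-serious solicited event that begins after rescue and is judged due to metronidazole.

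- Protocol 9.2.2 and SAP 4.5.1: not collected.
- Protocol 9.2.1 (documentation regardless of relationship): documented.
- Protocol 9.2.5 (all AE/SAEs): reported.
- Protocol 9.2.1 (the relationship assessment does not decide reporting): points the same way, but it speaks only of relationship to study product, so it is weaker support.
- Transfer to the unsolicited form: not stated anywhere.

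**Is auranofin still present at rescue?** Protocol 2.3.1 puts three half-lives at 4 months in total. Protocol 9.2.2 puts three half-lives within 28 days, or 28/3 = 9.3 days each. Even on the shorter figure, the Day 14 visit falls 14 − 7 = 7 days after the last amebiasis dose and 14 − 5 = 9 days after the last giardiasis dose. Both are less than one half-life, so drug is probably present on either figure.

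**Size.** No figure in the plan is at stake, so there is nothing to reproduce. The illustration borrows the design rates of Protocol 11.2. For amebiasis, "placebo is expected to have a clearance rate of approximately 15-20"%, against at least 80% on auranofin. For giardiasis, 30% on placebo against 70%. Each arm has 34 subjects.

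- Non-resolution f: amebiasis 0.20 on auranofin and 0.80 on placebo (taking the 20% end of the placebo range); giardiasis 0.30 and 0.70.
- Assumed, not in the documents: s, the share of non-resolvers rescued; p, the true solicited-event risk, equal in both arms; q, the share of rescued subjects' events attributed to metronidazole.
- Rescue rate r = s × f.
- Observed risk = p(1 − r·q).
- Spurious gap, auranofin minus placebo = p·q·s·(f placebo − f auranofin), where the bracket is 0.60 for amebiasis and 0.40 for giardiasis.

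| s | p | q | Amebiasis gap | Giardiasis gap |
|---|---|---|---|---|
| 0.10 | 0.20 | 0.5 | 0.6 points | 0.4 points |
| 0.10 | 0.40 | 1.0 | 2.4 | 1.6 |
| 0.25 | 0.20 | 0.5 | 1.5 | 1.0 |
| 0.25 | 0.40 | 1.0 | 6 | 4 |
| 0.50 | 0.20 | 0.5 | 3 | 2 |
| 0.50 | 0.40 | 1.0 | 12 | 8 |

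In the last amebiasis row, observed risk is 0.40(1 − 0.10) = 36% on auranofin and 0.40(1 − 0.40) = 24% on placebo. Subjects lost are 34 × 0.40 × 0.10 = 1.4 and 34 × 0.40 × 0.40 = 5.4. At the 15% end of the placebo range the bracket becomes 0.85 − 0.20 = 0.65 and the gap 0.40 × 1 × 0.50 × 0.65 = 13 points.

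The model counts every event in a rescued subject as open to exclusion. Events before rescue would in fact be kept, so the larger rows lean high.

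**Direction.** If the arms differ in p and q, the shift in the gap is (p·q·r on placebo) − (p·q·r on auranofin). It is positive, making auranofin look worse, when mainly placebo events are lost. It is negative, hiding auranofin toxicity, when auranofin's own effects are put down to metronidazole often enough to outweigh the difference in rescue. Nor is it certain that rescue follows the design failure rates: loose stools are auranofin's most frequent listed effect (42% in Protocol 2.3.1, 47% in 9.1, mostly longer-term use) and could themselves prompt rescue.

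**The case against.** The strongest defence is that the sentence is a deliberate exception. Metronidazole's own effects are not auranofin's, and counting them would load the arm with more rescue. That has force. Suppose a base risk of 20% and an added 40% chance of an event in rescued subjects, with half of non-resolvers rescued. Collecting everything then gives an amebiasis gap of 0.8 × 0.40 × (0.10 − 0.40) = −9.6 points. An all-events table alone is therefore not enough. But the exclusion corrects this only if attribution is accurate, and the plan gives no basis for that.

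A second defence is that such events may go to the unsolicited form, which is elicited by interview (Protocol 8.1) and records an alternate etiology (Protocol 9.2.1). This would reconcile the texts. Neither document says so; it shows that loss is the result of the rule as written, not a certainty in practice.

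Several stronger readings are tempting, and the documents do not support them.

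- A reader might treat all non-resolvers as rescued, giving placebo-to-auranofin ratios of 0.80/0.20 = 4 and 0.70/0.30 = 2.3. Rescue is discretionary and for worsening, not persistence. Non-resolvers are only an upper bound on the pool rescued by the endpoint day.
- A reader might cite nausea and vomiting as effects shared by both drugs. Protocol 2.3.2 ties them, for metronidazole, to alcohol ingestion.
- A reader might infer that the attributing physician knows the arm. Protocol 5.3.2 says only that personnel could detect capsule differences; SAP 4.4.1 and 4.4.3 describe identical bottles and staff not told of those differences.
- A reader might infer that Grade 3 events would be kept from the DSMB by this sentence. Notification in Protocol 9.4.1 requires a drug-related event, so one judged due only to metronidazole would not trigger it even if collected.

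**Conclusion.** The contradiction stands. It is firmest against the documentation rule in Protocol 9.2.1 and the all-events rule in 9.2.5. The passages must be reconciled.

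The by-arm solicited tables can be distorted, but neither size nor direction can be fixed from the documents. With no true difference, equal p and q in both arms and rescue proportional to design non-resolution, the spurious gap is 0.4-2.4 points at 10% rescue and reaches 12 points in amebiasis under strong assumptions. At low rescue rates it is minor.

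The reach is limited. The sentence covers solicited events only; SAEs, unsolicited events and laboratory events are outside it. Tables 35-36 carry no between-arm test. This should be fixed, but it is not a fundamental defect.

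**What to change.** Delete the exclusion sentence in Protocol 9.2.2 and in SAP 4.5.1. Collect all solicited events through Day 28 whatever the suspected cause, leaving the separate rule on diarrhea as it stands. Derive a flag for onset on or after the first metronidazole dose, using the concomitant-medication dates and the event start dates already required by Protocol 9.2.1. Present Tables 35-36 for symptomatic subjects twice: all events, and events with onset before any metronidazole. The second version has less time at risk where rescue is more frequent, so give the number rescued per arm beside it. That number also helps readers judge the possible loss among subjects already followed under the present rule.

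The cost is one derived flag and one extra version of two tables. No visit or procedure is added, because solicited symptoms and concomitant medications are already recorded, and the rescue provision itself is untouched.
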